5.2.2.2 CX-2009 Dosing – Parts D1 and D2

CX-2009 is planned to be administered in combination with CX-072 800 mg every 14 days in Parts D1 and D2 of study CTMX-M-2009-001. To match the every 14-day dosing schedule of CX-072, CX-2009 is likewise planned to be dosed every 14 days. The starting dose for CX-2009 will be set at the every 14-day monotherapy RP2D as determined in Part C1. Lower starting doses may be used based on emerging safety data and in consultation with the SRC.

5.2.3 CX-2009 + CX-072 as Combination Therapy Every 21 Days, Dose Escalation (Part E1) and Expansion (Part E2)

5.2.3.1 CX-072 Dose – Parts E1 and E2

A fixed dose of 1200 mg CX-072 administered every 21 days, which is equivalent to the 800 mg every 14-day dose, is planned for combination with CX-2009 in Parts E1 and E2 of study CTMX-M-2009-001.

5.2.3.2 CX-2009 Dosing – Parts E1 and E2

CX-2009 is planned to be administered in combination with CX-072 1200 mg every 21 days in Parts E1 and E2 of study CTMX-M-2009-001. To match the every 21-day dosing schedule of CX-072, CX-2009 is likewise planned to be dosed every 21 days. The starting dose of CX-2009 when administered with 1200 mg CX-072 every 21 days in Part E1 of study CTMX-M-2009-001 is to be the CX-2009 every 21-day monotherapy RP2D of 7 mg/kg.

5.3 Randomization and Blinding

This is an open-label study. No blinding is needed.

5.4 Breaking the Blind

This is an open-label study. No blinding is needed.

5.5 Drug Supplies and Administration

5.5.1 Formulation and Packaging

CX-2009

CX-2009 will be supplied as a lyophilized powder (cake) in 25 mg vials to be reconstituted with 5 mL of sterile water for injection (WFI) to a final concentration of 5.0 mg/mL. The label for CX-2009 will include standard product information. It will also include: CAUTION: New Drug – Limited by Federal (or United States) Law to Investigational Use. For Clinical Trial Use Only. Return all unused study medication.

CX-072

CX-072 drug product is currently being supplied as a sterile solution for IV administration. CX-072 is supplied in a 10 mL volume, and each vial contains 100 mg of CX-072 formulated with suitable compendial excipients. Upon regulatory approval, the CX-072 drug product is planned to be supplied as a lyophilized powder (cake) in single-use vials for reconstitution with sterile WFI before IV administration. The stability of the drug product is monitored according to the International Council for Harmonisation (ICH) Guidelines. The period of use of CX-072 drug product will be managed based on the evaluation of real time stability data.

5.5.2 Study Drug Preparation and Dispensing

Complete study-specific preparation and dispensing instructions for CX-2009 and CX-072 are described in their respective Pharmacy Manuals.

5.5.3 Study Drug Administration

Study drugs include CX-2009 and CX-072.

Study drugs will be administered on an outpatient basis, with inpatient admission as needed for any treatment or monitoring outside of clinic hours or for management of significant acute toxicity. See Section 5.5.3.1 for management of IRRs.

All doses will be administered through an IV line containing a sterile, nonpyrogenic, low protein binding in-line filter (pore size of 0.2 µm) and administered as an IV infusion controlled by a volumetric pump.

Do not co-administer other drugs through the same IV line during the study drug infusion. Study drugs should be administered under the supervision of a physician or other study personnel experienced in the use of IV agents.

When CX-2009 and CX-072 are administered on the same day, CX-072 is to be administered first, followed by a saline flush, followed by the CX-2009 infusion. CX-2009 is to be infused no sooner than 30 minutes after completion of the CX-072 infusion.

Additional information on study drug administration can be found in the Pharmacy Manual.

CX-2009

CX-2009 will be administered as an IV infusion over 90 (± 10) minutes with careful monitoring of IRRs. Following completion of the infusion, flush with an adequate amount of normal saline for infusion.

The SRC can modify the infusion rate for any dose if a \leq Grade 2 IRR occurs or if it is deemed to improve safe administration of CX-2009. If a \geq Grade 3 IRR occurs, this Module may be amended.

Do not administer CX-2009 as IV push or bolus injection.

CX-072

800 mg and 1200 mg CX-072 are to be infused over 60 (± 10) minutes. Following completion of the infusion, flush with an adequate amount of normal saline for infusion.

5.5.3.1 Management of IRRs

Subjects should not receive any premedication prior to infusions, unless it is determined during the course of the study (by the SRC/Sponsor) that the occurrence of IRRs warrants routine prophylactic treatment (which might include paracetamol/acetaminophen, histamine antagonists, and/or corticosteroids).

Individual subjects who do experience a \geq Grade 2 IRR may receive premedication prior to subsequent treatment cycles after review with the Medical Monitor.

For allergic (hypersensitivity) reactions occurring during or after study drug (CX-2009 or CX-072) administration, follow the guidelines in [Table 7](#).

Table 7. Management of Allergic Reactions

Grade of Allergic Reaction	Treatment
Grade 1: Transient flushing or rash, drug fever <38°C (<100.4°F)	Remain at bedside and monitor subject until recovery from symptoms.
Grade 2: Intervention or infusion interruption indicated; responds promptly to symptomatic treatment (eg, antihistamines, NSAIDs, narcotics); prophylactic medications indicated for ≤24 hours	
Stop the study drug infusion, begin an IV infusion of normal saline and treat the subject as follows:
 
 • Administer diphenhydramine 50 mg IV (or equivalent) and/or paracetamol/acetaminophen 325-1000 mg PO; remain at bedside and monitor subject until resolution of symptoms. Corticosteroid therapy may also be administered as appropriate. • If the infusion is interrupted, then restart the infusion at 50% of the original infusion rate when symptoms resolve; if no further complications ensue after 30 minutes, the rate may be increased to 100% of the original infusion rate. • Monitor subject closely. If symptoms recur then the infusion should be discontinued and no further study drug will be administered at that visit. Administer diphenhydramine 50 mg IV and remain at bedside and monitor the subject until resolution of symptoms. 
Premedication (diphenhydramine and paracetamol/acetaminophen) may be given prior to subsequent treatment cycles after review with the Medical Monitor.

Grade 3: Prolonged (eg, >6 hours, not rapidly responsive to symptomatic medication and/or brief interruption of infusion); recurrence of symptoms following initial improvement; hospitalization indicated for clinical sequelae (eg, renal impairment, pulmonary infiltrates)	
Immediately discontinue infusion of study drug. Begin an IV infusion of normal saline, and treat the subject as follows:
 
 • Recommend bronchodilators, epinephrine 0.2-1 mg of a 1:1000 solution for subcutaneous administration or 0.1-0.25 mg of a 1:10,000 solution injected slowly for IV administration, and/or diphenhydramine 50 mg IV with methylprednisolone 100 mg IV (or equivalent), as needed. • Subject should be monitored until the Investigator is comfortable that the symptoms will not recur. • Study drug will be permanently discontinued unless continuation of therapy is believed to provide potential clinical benefit and no other reasonable alternatives exist, then re-challenge may be pursued at the discretion of the Investigator after consultation with the Medical Monitor. • Investigators should follow their institutional guidelines for the treatment of anaphylaxis.
Grade 4: Life-threatening consequences; urgent intervention indicated.	Follow treatment for Grade 3 allergic reaction and monitor subject until recovery from symptoms. Study treatment will be permanently discontinued.

IV = intravenous; NSAID = nonsteroidal anti-inflammatory drug; PO = *per os*, oral.

During an IRR, vital signs will be obtained every 2 to 5 minutes until stable. In the case of late-occurring hypersensitivity symptoms (eg, appearance of a localized or generalized pruritus within 1 week after treatment), symptomatic treatment may be given (eg, oral antihistamine or corticosteroids).

5.5.3.2 Ocular Toxicity

All subjects enrolled in this study must adhere to the following impactful safety measures for the duration of CX-2009 exposure and 21 days after the last dose of CX-2009:

- Avoiding use of corrective contact lenses and switch to corrective glasses throughout the subject's time of participation in the study. Bandage contact lenses may be considered if prescribed by the treating ophthalmologist;
- Wearing ultraviolet A/ultraviolet B sunglasses whenever outdoors, even for short periods of time;
- Using preservative-free artificial tear eye drops for lubrication 3 times daily, starting at least 1 hour after the use of medicated eye drops; and
- All prophylactic measures for the eye during and post-infusion of CX-2009 listed below.

The following protective measures are required for all subjects to potentially reduce the exposure of the corneal limbal stem cells/transient amplifying cells to CX-2009 during and post-infusion:

1. Topical vasoconstrictor eye drops will be administered to both eyes, starting on the day of the infusion, 1 hour prior to each infusion of CX-2009. Brimonidine tartrate ophthalmic solution 0.025% (in the United States) should be administered to both eyes every 6 to 8 hours for 3 days, and brimonidine tartrate ophthalmic solution 0.2% (in Europe) should be administered to both eyes every 12 hours for 3 days, starting 1 hour prior to each infusion of CX-2009. If brimonidine tartrate ophthalmic solution is not available, tetrahydrozoline eye drops 0.05%, or naphazoline eye drops 0.025% may be used. If none of these agents are available or are not medically appropriate, suitable alternatives may be considered by the treating ophthalmologist, provided approval is granted by the Medical Monitor. Vasoconstrictor eye drops may be continued for longer if instructed by the treating ophthalmologist;
2. A cool compress will be applied to the eyes at the time of the infusion and continued for at least 2 hours and as much as tolerated on the day of the infusion; and
3. Topical steroid drops (such as prednisolone acetate eye drops, 1.0% or its equivalent), will be instilled in both eyes at least 30 minutes prior to CX-2009 infusion, and continued 4 times a day for 7 days. In addition, subjects may elect to use a topical ophthalmic steroid ointment at bedtime for 7 nights, starting the day of each CX-2009 infusion. In place of steroid ointment, a subject may consider artificial tears ointment or simply use artificial tears before bedtime. Treatment with topical steroid eye drops and the optional ointment may be continued longer if instructed by the treating ophthalmologist.

Subjects should contact the oncology team as soon as any ocular symptoms are experienced (eg, blurred vision), which will prompt an ophthalmology evaluation. The oncology team may consider initiating treatment with prolonged therapy with steroid eye drops, unless there is

suspicion of infectious conjunctivitis. The Medical Monitor should be informed if ocular symptoms necessitating ophthalmology evaluation are observed.

If ocular toxicity occurs, see Section 5.5.4.1.

5.5.4 Treatment Delays, Dose Modification, and Missed Doses

Treatment or visit delays for public holidays, weather conditions, or other unforeseeable circumstances (including toxicity considered unrelated to study treatment) do not constitute a protocol violation. However, delayed visits should be completed at the first available opportunity.

There must be a minimum of 21 days (Parts A, A2, B, E1, and E2) or 14 days (Parts C1, C2, D1, and D2) between study drug infusions (a window of ± 2 days may occur). In exceptional circumstances, an infusion may be delayed for up to 7 days. Infusions that cannot be administered in that timeframe will be considered a missed dose, and the subject's next planned dose should be 42 days (every 21-day dosing regimen; Parts A, A2, B, E1, and E2) or 28 days (every 14-day dosing regimen; Parts C1, C2, D1, and D2) after the last administered dose. A subject will be considered to have experienced a prolonged treatment delay and study drug will be discontinued if the subject misses 2 consecutive infusions, except as provided for in Section 5.5.4.1 and Section 5.5.4.2.

Subjects benefitting from treatment may be allowed longer treatment delays after discussion with the Medical Monitor. Subjects should be assessed for resolution of toxicity (eg, by scheduled physical examination, laboratory testing, etc.) at a frequency deemed by the Investigator to be appropriate for the specific clinical situation.

5.5.4.1 Dose Management for CX-2009

Dose delay or permanent discontinuation of CX-2009 may be required as dictated in [Table 8](#) and [Table 9](#).

Note: Where CX-2009 and CX-072 are administered in combination (Parts D1, D2, E1, and E2), if, in the opinion of the Investigator, a toxicity is considered to be due solely to one component of the study treatment (ie, CX-2009 or CX-072) and the dose of that component is delayed, modified, or permanently discontinued in accordance with the guidelines in the Module, the other component may be administered if there is no contraindication.

Table 8. CX-2009 Dose Modifications for Select Adverse Events

Adverse Event	Grade 1	Grade 2	Grade 3	Grade 4
Anemia	No action	No action	Hold until recovery to ≤Grade 2 with transfusion; re-challenge at same dose. ^a	Hold until recovery to ≤Grade 2 with transfusion; re-challenge at same dose ^a if Grade 4 recurs, permanently discontinue CX-2009.
Neutropenia	No action	No action	Hold until recovery to ≤Grade 2; re-challenge at same dose. ^a	Hold and consider supportive measures until recovery to ≤Grade 2; re-challenge at same dose. ^a
Thrombocytopenia	No action	No action	PLT 25,000/mm ³ – <50,000 mm ³ Hold until platelet count recovers to ≤Grade 1 and then treat at same dose level.	PLT <25,000/mm ³ Hold until platelet count recovers to ≤Grade 1 and then treat at same dose level.
Increased serum transaminases (AST/ALT) Note: Corticosteroids may be considered for the management of liver enzyme elevations	No action	No action	Hold until AST/ALT recovers to ≤Grade 2 and then treat at same dose level.	Permanently discontinue CX-2009.
Hyperbilirubinemia	No action	Hold until total bilirubin recovers to ≤Grade 1 and then treat at same dose level.	Hold until total bilirubin recovers to ≤Grade 1 and then treat at same dose level.	Permanently discontinue CX-2009.
Peripheral neuropathy (sensory motor)	No action	For new or worsening Grade 2 neuropathy, hold CX-2009 until neuropathy improves to Grade 1 or baseline.	For new or worsening Grade 3 neuropathy, hold CX-2009 until neuropathy improves to Grade 1 or baseline. Restart at same dose level. ^a Please note that a dose reduction may be considered in consultation with the Medical Monitor. Discontinue treatment permanently if no improvement within 2 weeks.	For new or worsening Grade 4 neuropathy, hold CX-2009 until neuropathy improves to Grade 1 or baseline. Please note that a dose reduction may be considered; consultation with the Medical Monitor is required. Discontinue treatment permanently if no improvement within 2 weeks.
Life-threatening or Grade 4 reaction	NA	NA	NA	Permanently discontinue CX-2009.

^a Please note that dose reduction may be considered following consultation with the Medical Monitor.

ALT = alanine aminotransferase; AST = aspartate aminotransferase; NA = not applicable; PLT = platelet count.

Neutropenia. Neutropenia should be managed by dosing delays. The dose of CX-2009 should be held for Grade 3 or Grade 4 neutropenia until resolution to baseline or ≤Grade 2. Growth factor support should be considered for subsequent cycles in subjects who experience Grade 3 or Grade 4 neutropenia. In subjects with recurrent Grade 4 neutropenia despite the use of growth factors, discontinuation of CX-2009 should be considered.

The dose of CX-2009 should be held for Grade 3 AEs judged by the Investigator to be treatment-related that are not listed in Table 8 until resolution to baseline or Grade 0.

In the event of a major surgery (any intervention requiring more than local anesthesia), stop dosing; resume dosing after consultation with the Medical Monitor.

Ocular Toxicity. In addition to the scheduled examinations, subjects who report new ocular symptoms will undergo repeat examinations as clinically indicated as well as prior to infusion every other cycle (every 42 days for Parts A, A2, B, E1, and E2; every 56 days for Parts C1, C2, D1, and D2). Management of treatment-emergent ocular disorders should include corticosteroid eye drops and/or other measures as indicated by the treating ophthalmologist. For steroid-refractory symptoms, the treating ophthalmologist may recommend other modalities, including higher dose topical corticosteroids, topical cyclosporine, or lifitegrast. These agents are not mandatory but may be used based on the treating ophthalmologist’s recommendation. Management of treatment-emergent ocular disorders is described in detail in Table 9.

Table 9. Management of Treatment-emergent Ocular Disorders

Category	Management	Guidelines for CX-2009 Dose Modifications
Category A: Symptomatic but no impact on ADL	
 •Complete eye examination as outlined in Appendix B; •Ensure protective measures for the eye are being utilized as described in Section 5.5.3.2; •Monitor for worsening symptoms; and •Subjects should have weekly ocular assessments until the symptoms resolve to baseline or are deemed to be irreversible by the Investigator. 	Continue CX-2009 dosing.
Category B: Symptomatic impact on ADL including preparing meals, shopping for groceries or clothes, using the telephone, or managing money	
 •Complete eye examination as outlined in Appendix B. Repeat complete examination as clinically indicated; •Ensure protective measures for the eye are being utilized as described in Section 5.5.3.2; •Monitor for worsening symptoms; •Treatment with corticosteroid eye drops and/or topical ophthalmic steroid ointment at bedtime and/or other measures as indicated by the treating ophthalmologist; and •Subjects should have weekly ocular assessments until the symptoms resolve to baseline or are deemed to be irreversible by the Investigator. 	Hold CX-2009 dosing until there is no longer a symptomatic impact on ADL. If a dose is needed to be held due to symptomatic impact on ADL for <2 weeks, resume dosing at the same dose level. If a dose is needed to be held due to symptomatic impact on ADL for > 2 weeks, dose reduction is required.
Category C: Symptomatic impact on self-care ADL (including bathing, dressing and undressing, feeding self, using the toilet, taking medications, and not bedridden)	
 •Complete eye examination as outlined in Appendix B. Repeat complete examination as clinically indicated; •Ensure protective measures for the eye are being utilized as described in Section 5.5.3.2; •Treatment with corticosteroid eye drops and/or topical ophthalmic steroid ointment at bedtime and/or other measures as indicated by the treating ophthalmologist; and •Subjects should have weekly ocular assessments until the symptoms resolve to baseline or are deemed to be irreversible by the Investigator. 	Hold CX-2009 dosing until there is no longer a symptomatic impact on ADL. Dose reduction is required. A permanent discontinuation consideration should be made with the Investigator, ophthalmologist, and after discussion with the Medical Monitor.

ADL = activities of daily living.

Dose Reduction. Dose reduction steps are outlined in [Table 8](#) and [Table 9](#). In cases where [Tables 8](#) or [9](#) do not indicate a dose reduction, a dose reduction may be approved with consultation of the Medical Monitor. There cannot be more than 42 days (every 21-day dosing regimen; Parts A, A2, B, E1, and E2) or 28 days (every 14-day dosing regimen; Parts C1, C2, D1, and D2) between dosing unless approved by the Medical Monitor (see [Section 5.5.4](#)).

In Parts C1 and C2, as a first step, CX-2009 dose may be reduced to a dose level below the assigned starting dose. Should the AE reoccur after the first dose reduction, a further dose reduction (by another 1 mg/kg reduction) can be attempted if clinically beneficial and following consultation with the Medical Monitor. No subsequent dose escalation of CX-2009 will be authorized for subjects who have had a dose reduction for safety reasons.

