1.3.4.1 Summary of CX-2009 Clinical Safety

A total of 92 subjects treated with CX-2009 had available safety data. All but 6 subjects received CX-2009 once every 21 days at doses ranging from 0.25 mg/kg to 10 mg/kg. Six subjects received CX-2009 once every 14 days at a dose of 6 mg/kg. Please refer to the Investigator's Brochure (IB) for the most up-to-date information.

Overview of Treatment-emergent Adverse Events

Approximately 91.3% (84 of 92) of subjects had adverse events (AEs) that were judged by the Investigator to be related to study treatment. Forty-two (45.7%) had ocular toxicity that was related to CX-2009, with symptoms similar to other DM4 ADCs.

Twenty-six (28.3%) subjects experienced peripheral neuropathy related to CX-2009. The majority (13/26) had events that were Grade 1. Five subjects had Grade 3 peripheral neuropathy related to CX-2009.

Twenty (21.7%) subjects experienced infusion-related reactions (IRRs), the majority of which were Grade 1 or 2 (1 subject had a Grade 3 IRR). A previous analysis noted that the majority of subjects who had an IRR at the first infusion cycle, did not experience recurrence at subsequent infusions when premedication was administered.

Treatment-related SAEs and Treatment-related AEs Grade 3 or Higher

Eleven (12.0%) subjects experienced treatment-related serious adverse events (SAEs). Thirty-four (37.0%) subjects experienced Grade 3/4 treatment-related adverse events (TRAEs), including 10 with ocular toxicity (n = 8 Grade 3, n = 2 Grade 4) and 5 with peripheral neuropathy (all Grade 3).

There was 1 death related to study treatment according to Investigator's assessment.

Refer to the most recent version of the CX-2009 IB for the most updated and complete safety data.

Dose-Limiting Toxicities

One DLT was observed in Part A (8 mg/kg every 21 days); a Grade 3 event of vomiting that resolved (22 subjects were treated at this dose and schedule). No DLTs were observed at 9 and 10 mg/kg in 9 and 8 subjects, respectively.

Three DLTs were reported in 2 out of 5 evaluable subjects who received CX-2009 at a dose of 6 mg/kg every 14 days (Part C1) including a Grade 3 increased aspartate aminotransferase (AST) and a Grade 3 increased alanine aminotransferase (ALT) in 1 subject, and a Grade 3 peripheral neuropathy in another subject.

Treatment-emergent Adverse Events Related to CX-2009 at the Every 21-day Monotherapy RP2D of 7 mg/kg

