3.3 Dose-Limiting Toxicity

All AEs will be captured according to the National Cancer Institute Common Terminology Criteria for Adverse Events (NCI CTCAE) v4.03 (and considered for assessment of DLTs as outlined by the criteria in [Table 5](#)).

Table 5. Dose-Limiting Toxicity

Suspected DLT Criteria	DLT	
	Yes	No
Grade 5 AEs judged by the Investigator to be treatment-related or judged by the Sponsor as treatment-related, regardless of Investigator attribution.	X	
Grade 4 AEs* judged by the Investigator to be treatment-related or judged by the Sponsor as a DLT, regardless of Investigator attribution.	X	

*Grade 4 Exceptions
 
 • The following Grade 4 hematologic AEs: 
 – Grade 4 lymphopenia; and – Grade 4 neutropenia lasting <7 days that is not associated with fever, or other clinically significant symptoms, or is corrected with supportive measures (eg, growth factors)/appropriate management. • Grade 4 electrolyte imbalances/abnormalities that are not associated with clinical sequelae and are corrected with supplementation/appropriate management within 72 hours of their onset. 		X

Grade 3 AEs** judged by the Investigator to be treatment-related or by the Sponsor, regardless of Investigator attribution, including:
 
 • Any Grade 3 AE that does not resolve to Grade ≤1 or to baseline with appropriate therapies within 7 days of onset; • Any Grade 3 febrile neutropenia; • Any clinically significant Grade 3 CNS event; • Any Grade 3 neurotoxicity; and • Any Grade 3 ocular toxicity (limiting self-care ADL) that does not resolve within 7 days and which did occur despite proper application of preventive measures. 	X	

**Grade 3 Exceptions
 
 • Isolated Grade 3 electrolyte imbalances/abnormalities that are not associated with clinical sequelae and are corrected with supplementation/appropriate management within 72 hours of their onset; • Grade 3 asthenia which persists for up to 7 days; • “Tumor flare” – defined as local pain, irritation, or rash localized at sites of known or suspected tumor; and • Grade 3 infusion reaction which resolves to ≤Grade 1 within 6 hours. 		X
Grade 2 pneumonitis, Guillain-Barré syndrome, transverse myelitis, myocarditis, pericarditis, and arrhythmias necessitating discontinuation of CX-072.	X	

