5.5.9 Discontinuation of CX-2009 for Adverse Events

Subjects with Grade 4 AEs requiring permanent discontinuation of CX-2009 as described in [Table 8](#) and [Table 9](#) must be discontinued. Subjects who fail to resolve AEs as described in

Section 5.5.6 must be discontinued unless a discussion between the Investigator and Medical Monitor documents that a further period of waiting for resolution is warranted.

Where CX-2009 and CX-072 are administered in combination (Parts D1, D2, E1, and E2), if, in the opinion of the Investigator, a toxicity is considered to be due solely to one component of the study treatment (ie, CX-2009 or CX-072) and the dose of that component is delayed, modified, or permanently discontinued in accordance with the guidelines in the Module, the other component may be administered if there is no contraindication.

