8.2.2 Severity

The severity of an event describes the degree of impact upon the subject and/or the need for, and extent of, medical care necessary to treat the event.

AE grading will be defined by the NCI CTCAE v4.03. In the event that the NCI CTCAE v4.03 does not apply, the severity descriptions in [Table 11](#) will be used to describe the maximum intensity of the AE.

Table 11. Adverse Event Severity

Grade	Description
Grade 1	Mild; asymptomatic or mild symptoms; clinical or diagnostic observations only; intervention not indicated
Grade 2	Moderate; minimal, local or noninvasive intervention indicated; limiting age-appropriate instrumental activities of daily living.
Grade 3	Severe or medically significant but not immediately life-threatening; hospitalization or prolongation of hospitalization indicated; disabling; limiting self-care activities of daily living
Grade 4	Life-threatening consequences; urgent intervention required
Grade 5	Death related to an adverse event

Source: https://www.eortc.be/services/doc/ctc/CTCAE_4.03_2010-06-14_QuickReference_5x7.pdf. Accessed 19 November 2019.

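### Section 5.5.4.1 sets two different restart thresholds for the same Grade 3 ocular event and leaves unclear which rule covers a Grade 4 ocular event

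*Protocol*

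**What the plan says.** Four places in the Protocol bear on restarting or stopping CX-2009 after a severe eye event.

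- **Section 5.5.4.1, text below Table 8.** For events of Grade 3 severity, CX-2009 is withheld in the case of "AEs judged by the Investigator to be treatment-related that are not listed in Table 8 until resolution to baseline or Grade 0". Table 8 has rows for haematological, hepatic and neuropathic events and a general Grade 4 row. It has no ocular row.
- **Section 5.5.4.1, Table 9, Category C** (symptoms affecting self-care). The instruction is "Hold CX-2009 dosing until there is no longer a symptomatic impact on ADL. Dose reduction is required". Permanent discontinuation is to be considered together with the ophthalmologist and the Medical Monitor. The mildest category, A, is "Symptomatic but no impact on ADL", and dosing continues there.
- **Section 5.5.4.1, Table 8, last row.** For a "Life-threatening or Grade 4 reaction" CX-2009 is permanently discontinued.
- **Section 5.5.9.** "Subjects with Grade 4 AEs requiring permanent discontinuation of CX-2009 as described in" Tables 8 and 9 must be discontinued.

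Section 5.5.4.1 opens by naming both tables as the source for delays and discontinuations, and later names Table 9 as the detailed guidance for eye disorders. The SAP does not address the question.

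**The concern.** A site managing a Grade 3 eye event can follow the Module faithfully and reach either of two restart points. A site managing a Grade 4 eye event cannot tell from the text whether stopping is mandatory or only to be considered. These are instructions for sight-affecting toxicity in a study where ocular findings also informed the choice of the every-21-day dose (Section 5.2.1.2).

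There is a possible knock-on for the data. The length of a hold determines whether a dose counts as missed under Section 5.5.4, and interruptions are monitored in the dose-finding and expansion parts.

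**Working it through.** **1. Does Category C correspond to Grade 3?** Table 5 describes the ocular DLT as "Any Grade 3 ocular toxicity (limiting self-care ADL) that does not resolve within 7 days", and Table 11 defines Grade 3 as, among other things, "limiting self-care activities of daily living". Category C is symptomatic impact on self-care. By the Module's own wording, the two describe the same event.

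**2. Grade 3, rules side by side.**

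| | Text below Table 8 | Table 9, Category C |
|---|---|---|
| Applies to | Related Grade 3 AEs without a row in Table 8, hence eye events | Eye events affecting self-care |
| Hold ends when | Baseline or Grade 0 | No symptomatic impact on daily activities |
| Residual symptoms above baseline | Not allowed | Allowed (this is Category A, where dosing continues) |
| Dose at restart | Not stated in the sentence | Reduced |

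The thresholds differ whenever the impact on daily activities has ended but symptoms above baseline persist. They coincide if both end together. Table 9 also foresees symptoms judged irreversible. Read literally, the text rule would not let such a subject restart, whereas Table 9 could once daily activities are unaffected.

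**3. Grade 4.** The last row of Table 8 cannot apply to every Grade 4 event, because rows above it allow Grade 4 anemia, neutropenia, thrombocytopenia and neuropathy to be held, with treatment resumed under conditions. Its reach must therefore be limited, but no limit is written. The matching CX-072 row in Table 10 does state an exception for events listed above it. Table 9 has no Grade 4 entry, and its worst category asks only that discontinuation be considered. Section 5.5.9 nevertheless points to both tables for mandatory Grade 4 stops.

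**4. Frequency** (Section 1.3.4.1, data to 30 November 2019). The stated percentages reproduce: 42/92 = 45.7% with related ocular toxicity and 34/92 = 37.0% with Grade 3/4 related events. Among the latter are "10 with ocular toxicity (n = 8 Grade 3, n = 2 Grade 4"). Thus 8 + 2 = 10, and 10/92 = 10.9% of treated subjects. Five subjects had Grade 3 neuropathy.

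**5. Possible effect on missed doses.** Under Section 5.5.4 a delay of more than 7 days makes a missed dose. On every-21-day dosing the second dose falls on Day 22, so the limit is Day 22 + 7 = Day 29. Assume, for illustration, that impact on daily activities ends on Day 25 and symptoms clear on Day 35. Table 9 permits dosing on Day 25, a delay of 25 − 22 = 3 days. The text rule holds to Day 35, past Day 29, so the dose is missed.

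Whether the event count changes depends on onset. Suppose preventive measures were properly used and resolution means Grade 1 or lower, reached on Day 25. Onset by Day 17 gives 17 + 7 = Day 24 without resolution, which is already a DLT under Table 5 whichever restart rule is used. If resolution means complete clearing on Day 35, any onset in Days 1–21 is a DLT, since 21 + 7 = Day 28.

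**The case against.** The strongest reply is that Table 9 plainly governs eye events: it is the specific table, it follows the general sentence under its own ocular paragraph, and it has a dose-modification column. On that reading the sentence below Table 8 is residual and merely omits a reference to Table 9. This is a sensible inference, but the Module does not state it, and the sentence exempts Table 8 alone. The slip stands.

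On Grade 4, a reader might infer a head-on contradiction between Tables 8 and 9. The documents do not support that. Table 9 never mentions Grade 4, Table 8 gives an instruction that could be read as covering eye events, and Section 5.5.9 could be satisfied by Table 8 alone. What remains is unstated scope and a cross-reference to content that is absent.

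A reader might also infer that one reclassified subject changes a dose or enrolment decision. With six subjects, 1/6 = 16.7% and 2/6 = 33.3% do straddle the 20% expansion limit in Section 9. But the definition of interruption as a missed dose appears only for the Part A mTPI-2 cohort (Section 3.2), which closed in November 2019. The expansion rule does not define interruption, so a short hold might count too, and it has a further window after a dose reduction. The SAP reports that enrolment stopped on 07 July 2020 with 3 subjects in Part B and none in C2, D1 or D2.

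Variation between sites is also tempered. Eye disorders of Grade 3 or higher are reported within 24 hours (Section 8.7), and the Medical Monitor is involved in Category C discontinuation decisions and in longer delays.

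**Conclusion.** The point holds. For Grade 3 eye events there are two stated restart thresholds and no precedence rule. For Grade 4 eye events the scope of Table 8's last row is unclear, and Table 9 and Section 5.5.9 do not match. The Grade 3 finding rests on equating Category C with Grade 3, as Tables 5 and 11 do.

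The 10 of 92 subjects (10.9%) show how often such events arise. It would be tempting to say these cases were handled under conflicting rules, but nothing shows that the current wording applied to them. Nor is the figure a rate at the selected dose: at the 28 October 2019 cut, Section 5.2.1.2 places 9 Grade 3/4 ocular reports at 8 mg/kg every 21 days and above (with 6 mg/kg every 14 days included) and 1 Grade 3 report at 5 mg/kg. Calling ocular toxicity the main severe toxicity also goes too far. It is the larger of the two categories that Section 1.3.4.1 names, but the 34 subjects with Grade 3/4 related events are not fully itemised.

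An effect on missed-dose and interruption counts is possible, depending on onset date and hold length. It is not automatic. The end of enrolment limits the reach for future cohorts but does not reconcile the instructions themselves.

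**What to change.** Reconcile the text below Table 8, Table 8's last row, Table 9 and Section 5.5.9:

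1. State whether the sentence on Grade 3 events without a row in Table 8 applies to events covered by Table 9.
2. State whether the last row of Table 8 applies to events that have their own row or their own table.
3. Make Table 9 and Section 5.5.9 agree on Grade 4 ocular events, so that the cross-reference leads to an actual instruction.

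Which restart or stopping rule should apply is for the sponsor's clinical team and the SRC to decide. The cost is wording in two sections and their tables within a Module amendment, with no new procedures and no additional subjects.
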